10 STATISTICAL ANALYSES

10.1 Study Population

The number of patients planned to be randomized into this domain protocol is 72. This would allow for testing the validity of our eligibility criteria, ventilation protocols, and study procedures. It will also allow for an assessment of crossovers at numerous sites involving a number of clinicians. The sample size would allow for an assessment of feasibility objectives over a reasonable time period of 1 year as well as allow us to detect an adherence rate of 80% + 10% (meaning 80% + 10% of study patients will have fewer than 10% of monitored values as major deviations).

For the feasibility objectives of this pilot RCT we will present point estimates as proportions with 95% confidence intervals. We will present continuous data as means (standard deviations), or medians (interquartile ranges), as appropriate. We will not undertake formal statistical interference for any outcomes.

10.2 Evaluation of Safety

The safety and tolerability of VV-ECMO will be evaluated by means of recording SAEs in both groups and monitoring the predicted physiological response (reduced driving pressure ΔP) to CO₂ removal by VV-ECMO.

The following safety outcomes will be evaluated:

- Mechanical complications
- Hemorrhagic complications
- Renal complications
- Cardiovascular complications
- Pulmonary complications
- Metabolic complications
- Neurological complications
- Infections
- Death
- Clinical endpoints as defined in section 9.10.

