Statistical Analysis:	A target sample size of 72 ARDS patients will be randomized across sites given 1 year of active enrollment per site. This timeline will determine feasibility, as well as test the validity of our eligibility criteria, ventilation protocols, and study procedures. Descriptive statistical analyses and an intention-to-treat principle will be employed for the pilot phase of the trial.

TABLE OF CONTENTS

1	SYNOPSIS	4
2	List of Abbreviations	10
3	BACKGROUND	12
3.1	The problem to be addressed	12
3.2	Why is a trial needed now?.....	12
4	PRIMARY RESEARCH QUESTIONS AND STUDY OBJECTIVES	14
4.1	Definitive ULTIMATE Trial	14
4.2	The ULTIMATE Pilot Study	14
5	STUDY DESIGN	15
5.1	Patient population	15
5.2	PRACTICAL Platform Eligibility Criteria	15
5.2.1	PRACTICAL Inclusion Criteria.....	15
5.2.2	PRACTICAL Exclusion Criteria	15
5.3	ULTIMATE Domain Eligibility Criteria.....	16
5.3.1	Inclusion Criteria	16
5.3.2	Exclusion Criteria.....	16
5.4	Patient Consent.....	17
6	STUDY PLAN	18
6.1	Study Schedule.....	18
6.2	Study Schema.....	18
6.3	Optional Correlative Sample Collection	20
7	CONCOMITANT MEDICATION/ PROCEDURES	21
8	TRIAL INTERVENTIONS	22
8.1	Experimental Group: Ultra-protective Ventilation using ECMO devices.....	22
8.1.1	Stabilization and ECMO Initiation	22
8.1.2	Maintenance and Weaning of Ultra-Protective Ventilation	23
8.2	Control Group: Conventional Lung-Protective Ventilation (LPV)	24
8.3	Procedures Common to Both Groups – Experimental & Control	25
8.4	Crossovers.....	25

8.5	ECMO Study Device Supply	25
9	SAFETY AND REPORTING REQUIREMENTS	26
9.1	Serious Adverse Event	26
9.2	Reporting Serious Adverse Events	27
9.3	Procedures for Expedited Reporting	28
9.4	Reporting & Follow up of Serious Adverse Events	28
10	STATISTICAL ANALYSES	29
10.1	Study Population	29
10.2	Evaluation of Safety	29
10.3	Evaluation of Efficacy	30
10.4	Primary Objective	30
10.5	Primary Endpoint	30
10.6	Secondary Objectives	30
10.7	Secondary Endpoints	30
10.8	Exploratory Objectives	30
10.9	Exploratory Endpoints	31
10.10	Clinical Endpoints	31
10.11	Proposed Type of Analyses	31
10.12	Proposed Frequency of Analyses	31
10.13	Feasibility Outcomes	32
10.14	Sites	32
10.15	Randomization Scheme	32
11	PUBLICATION POLICIES AND DISCLOSURE OF DATA	33
11.1	Intellectual Property	33
11.2	Data Sharing	33
12	References	34

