8.1.1 Stabilization and ECMO Initiation

If not already done, patients will be deeply sedated to a Sedation Assessment Scale (SAS) = 1 and then be paralyzed with a neuromuscular blocking agent (NMBA). Baseline usual care standard ventilation will then be set as follows:

- Mode: Volume Assist-Control
- FiO₂ 1.0;
- PEEP 10-15 cm H₂O or higher as needed to maintain SpO₂>92%;
- V_T = 6 ml/kg PBW and adjusted to maintain P_{PLAT} ≤ 30 cm H₂O
- Inspiratory to expiratory (I:E) ratio 1:1 to 1:3, avoiding auto-PEEP
- Respiratory rate set to match previous minute ventilation to maximum of 35 bpm and targeting a pH above 7.15

These initial adjustments may occur over a period of a few minutes to a couple of hours, depending upon the baseline V_T and the ability of the patient to tolerate sudden changes. In keeping with routine clinical practices, an arterial blood gas should be drawn within 1 hour of transitioning onto the study protocol to assess both oxygenation and ventilation.

As soon as the patient is stable on these standard settings, the clinical team will measure the patient's respiratory elastance using the following equation:

$$Elastance = \frac{Driving\ Pressure}{\frac{Tidal\ Volume}{PBW}} = \frac{P_{plat} - PEEP\ total}{\frac{VT}{PBW}}$$

If the patient's static driving pressure is 15 cmH₂O or lower, then re-assess patient within a 12-hour timeline for ECMO initiation whilst keeping the patient deeply sedated and paralyzed. If patient's static ΔP is 16 cmH₂O or higher, then proceed with cannulation and connection to the VV-ECMO circuit using sterile technique and monitoring according to usual practice (e.g. ultrasound-guided puncture, radiography, trans-esophageal echocardiography (TEE), or

fluoroscopic cannula positioning). We recommend use of the study-supplied dual-lumen bicaval Crescent cannula connected to the Nautilus oxygenator, but the clinical team may choose any VV-ECMO configuration that facilitates 3-5 L/min blood flow.

VV-ECMO will then be initiated with pump speed set to deliver blood flow of 3-5 L/min and sweep gas flow of 1 L/min of 100% oxygen.

The mechanical ventilator will then be adjusted as follows:

- Mode: Pressure Control
- FiO₂ 0.5
- Set Driving Pressure to 10
- PEEP 10-15 cm H₂O
- Inspiratory time 0.7-1 second
- Respiratory rate 10

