8.2 Control Group: Conventional Lung-Protective Ventilation (LPV)

Patients randomized to the control group will be treated with the same explicit standard ventilation protocol that we used to good effect in several recent multi-centre trials in ARDS. The overall goals for this strategy are to minimize volutrauma and atelectrauma to the extent possible with standard of care ventilation.

Volume Assist Control will be the default mode and will be set to achieve lower tidal volumes (6ml/kg PBW) and plateau pressures ($P_{PLAT} \leq 30$ cm H₂O). Other modes may also be used at the discretion of the attending physician. The same limits to P_{PLAT} and V_T apply regardless of ventilator mode. Only when the patient is being ventilated with Pressure Support of 10 cm H₂O support or less and with PEEP ≤ 8 cm H₂O and FiO₂ ≤ 0.4 will these thresholds (P_{PLAT} and V_T) no longer apply. We recommend that PEEP and FiO₂ be adjusted according to oxygenation targets using the higher PEEP-FiO₂ table, allowing for use of lower PEEP if clinically indicated. If the plateau pressure target is exceeded, V_T will be reduced as needed to a minimum of 4 ml/kg PBW, and/or PEEP reduced and FiO₂ increased as necessary to achieve $P_{PLAT} \leq 30$ cm H₂O while providing adequate oxygenation.

If a patient's state worsens and meets entry criteria from the EOLIA trial (persistence of either $\text{PaO}_2/\text{FiO}_2 < 80$ or $\text{pH} < 7.15$ and $\text{PaCO}_2 > 60$) they can receive VV-ECMO (a secondary outcome) at the discretion of the attending physician.

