8.4 Crossovers

We will sub-classify crossovers as consistent with, or in deviation of, the study protocol and will collect detailed reasons for crossovers classified as protocol deviations. Crossovers that are consistent with the protocol include control group patients who receive the ECMO intervention (experimental group) once they meet the ECMO criteria of hypoxemia (section 7.2) and as part of rescue therapy, or when ECMO is discontinued before day 7 in the experimental group after passing a sweep gas off trial (section 7.1.2). Crossovers that are in deviation of the protocol will include Conventional Lung-Protective Ventilation (control group) patients being treated with ECMO when not allowed by protocol (do not meet the criteria defined in sections 7.2/3.2/3.3) and ultra-protective ventilation (experimental group) patients who stop the ECMO intervention prematurely.

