10.12 Proposed Frequency of Analyses

Due to the small size and short duration of this pilot RCT, we have not planned for any domain-specific interim analyses. We have planned, however, to provide the Data Safety and Monitoring Board (DSMB) with analyses by group at the completion of this pilot RCT. Further details regarding DSMB commitment will be detailed in the DSMB charter. These analyses will include relative use of neuromuscular blockade, sedative infusions, and vasopressor infusions; and relative rates of prone positioning, ECMO, and mortality. In this pilot RCT, we will not undertake any formal statistical inference or testing and will report descriptive statistics as required. We

will also consider controlling for centre and providing both unadjusted analyses and analyses adjusted for age and baseline oxygenation, and duration of ventilation prior to enrolment using Bayesian (generalized) linear models. The results from these models will be summarised using the posterior mean and 95% credible intervals. All these analyses will include all randomised patients adhering to the intention to treat principle. We will use complete case analyses, with the level of missingness reported for each outcome. Investigators will remain blinded to these clinical results, while the full ULTIMATE trial moves forward. Due to the pilot study design of the trial and its short duration, no subgroup analyses are planned.

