10.13 Feasibility Outcomes

- 1) Adherence to our explicit ventilation protocols will be adequate if more than 80% of patients have fewer than 10% of monitored values as major protocol deviations.
- 2) The number of protocol withdrawals or off-protocol treatment with VV-ECMO will be acceptable if fewer than 10% of patients cross over, when not allowed by protocol.
- 3) Patient accrual will be adequate if we recruit at least 60 patients over 1 year of active site enrolment.

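### Section 10.2 sets out to judge the safety of VV-ECMO itself but describes SAEs only by randomised group; a table by ECMO actually received should be added

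*Protocol*

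**What the plan says.** Section 10.2 of the Protocol names the device as the object of the safety evaluation: "The safety and tolerability of VV-ECMO will be evaluated by means of recording SAEs in both groups", together with the driving-pressure response. Section 10.9 lists the frequency and type of SAEs as an exploratory endpoint.

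The Synopsis gives the analysis principle: "Descriptive statistical analyses and an intention-to-treat principle will be employed for the pilot phase of the trial". Section 10.12 repeats it for the analyses listed there: "All these analyses will include all randomised patients adhering to the intention to treat principle". That list covers co-interventions, ECMO use, mortality and adjusted models. It does not name SAEs. No section describes a summary by ECMO received.

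Two rules separate assignment from exposure:

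- **Controls.** Under section 8.2, controls who deteriorate to the stated rescue criteria may be given ECMO: "they can receive VV-ECMO (a secondary outcome) at the discretion of the attending physician". Section 8.4 counts this as a crossover consistent with the protocol.
- **Experimental group.** Under section 8.1.1, if static driving pressure is 15 cmH2O or lower after stabilisation, the team is not to cannulate at that point: "then re-assess patient within a 12-hour timeline for ECMO initiation whilst keeping the patient deeply sedated and paralyzed". The section does not say what follows if the value stays there.

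Section 10.13 limits only the other kind of crossover: "acceptable if fewer than 10% of patients cross over, when not allowed by protocol". Rescue ECMO that the protocol allows has no limit.

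**The concern.** An event caused by ECMO can occur only in a patient who has been cannulated. Most of the SAEs of particular interest in section 9.1 are of this kind, such as device failure, circuit clotting and cannula-site complications. The natural denominator for a statement about the device is therefore the patients placed on ECMO.

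A by-arm table departs from this in two separate ways. Experimental patients who are never cannulated stay in the denominator and lower that arm's rate. ECMO events in rescued controls are counted in the control arm and shrink the difference between arms. For ECMO-caused events, both errors make the device look safer.

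What is at stake is the accuracy of a descriptive safety statement. Section 4.2 allows pilot patients to roll over into the definitive trial, so the reporting convention may carry forward.

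**Working it through.** **The plan's own figure.** The only sizing figure is N = 72, for estimating 80% adherence (section 10.1; the printed sign is read here as plus or minus 10 points). The Wald half-width is 1.96 × √(0.8 × 0.2 / 72) = 9.2 points, and the exact method needs 70 patients for 10 points, so the figure reproduces. It does not bear on safety, for which no sizing figure is given.

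**Inputs**

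- Patients per arm: 72 / 2 = 36, from 1:1 allocation (section 10.15).
- c, the risk of an ECMO-caused event per patient on ECMO: no planning value is given. For illustration, c = 6%, the hemolysis-or-bleeding figure that section 3.2 reports for the higher-flow device.
- u, the share of the experimental group never on ECMO: not given; assumed 0-30%.
- r, the share of controls given rescue ECMO: not given; assumed 0-30%.
- Simplifications: no ECMO-caused event off ECMO, and the same c for early and rescue ECMO.

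**Formulas**

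- Experimental-arm rate = c(1-u)
- Control-arm rate = c·r
- Difference = c(1-u) - c·r = c(1-u-r)

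**Results for c = 6%**

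| u | r | Experimental arm | Control arm | Difference | Difference / c |
|---|---|---|---|---|---|
| 0 | 0 | 6.0% | 0.0% | 6.0 points | 1.00 |
| 0 | 30% | 6.0% | 1.8% | 4.2 points | 0.70 |
| 10% | 10% | 5.4% | 0.6% | 4.8 points | 0.80 |
| 20% | 30% | 4.8% | 1.8% | 3.0 points | 0.50 |
| 30% | 30% | 4.2% | 1.8% | 2.4 points | 0.40 |

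Across the assumed range, the experimental-arm rate shows 70-100% of c and the difference shows 40-100%. The second row separates the two effects: with u = 0, rescue ECMO leaves the experimental-arm rate unchanged and moves only the difference.

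**Against chance.** Expected events among 36 patients on ECMO: 36 × 0.06 = 2.16. For 2 of 36 (5.6%), the exact 95% interval is 0.7% to 18.7%. The largest dilution in the table is 6.0 - 4.2 = 1.8 points for the arm rate and 6.0 - 2.4 = 3.6 points for the difference. The interval is 18.0 points wide, so sampling error is the larger problem. Dilution differs in that it is systematic, and the table by exposure avoids it.

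**The case against.** The strongest objection is that section 10.2 speaks of recording SAEs, not of analysing them in an intention-to-treat set, and that the list in section 10.12 omits SAEs. Safety sets are commonly left to the SAP, which is not at hand. This stands in part: a reader might infer that the protocol expressly fixes intention to treat for SAEs, but that rests only on the general sentence in the Synopsis. That sentence covers the whole pilot without exception, however, and no other basis for a device-safety statement is given.

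Second, much of the attribution is already built in. SAEs count only if judged related to a study procedure (sections 9 and 9.1), and section 8.4 says: "We will sub-classify crossovers as consistent with, or in deviation of, the study protocol". This is true, and it is why the change is cheap. It does not supply the missing denominator.

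Third, u may be small. Exclusion 3 in section 5.3.2 already removes patients with static driving pressure of 15 cmH2O or lower at 6 mL/kg, and re-assessment may still lead to ECMO. This stands; the range here is an assumption, not a forecast.

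Fourth, pooling everyone cannulated would mix early ECMO with rescue ECMO in patients who have deteriorated, and counting from cannulation would miss harm from sedation or paralysis before or without it. Both are fair. They are met by splitting the table by arm and keeping the by-arm table.

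Three stronger readings are tempting but not supported:

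- A reader might take the 27% in section 3.2 as ECMO's complication rate. It belongs to the comparator devices.
- A reader might quote one percentage as the understatement. Under this model it is simply u + r for whatever values are chosen.
- A reader might suppose that the figure decides the definitive trial or feeds consent forms. The criteria in section 10.13 are adherence, off-protocol crossover and accrual. None is an SAE rate, and nothing assigns the figure to consent forms.

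**Conclusion.** The point holds as one of reporting. Section 10.2 asks about the device, while the stated principle and the description of SAEs are by group, and the protocol's own rules let group and exposure diverge in both arms. For ECMO-caused events, a by-arm figure read as the device's complication rate errs towards looking safer.

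The direction follows from the protocol's rules; the size does not. The 70-100% and 40-100% ranges depend on the assumed 0-30% for u and r, on no such events off ECMO, and on equal risk in early and rescue ECMO. With about 2 expected events at c = 6%, chance exceeds the dilution.

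By-arm reporting remains right for comparing the two strategies, including mortality. No formal inference is planned, and N does not change.

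**What to change.** Keep the by-arm SAE table for comparing the strategies, including SAEs that occur before or without cannulation. In sections 10.2 and 10.9, add a descriptive table of ECMO-related SAEs among all patients actually cannulated:

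- counted from cannulation onward, per patient and per ECMO-day;
- shown separately for experimental-arm ECMO and control-arm rescue ECMO;
- labelled as a non-randomised grouping.

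State that the conclusion on the device's safety rests on this table, and add to the Synopsis that safety is also summarised by treatment received. Also state whether rescue ECMO in a control counts as a study procedure under section 9.1. If it does not, section 9 could leave those SAEs uncollected and the control-arm part of the table empty.

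The cost is one table and a few sentences. Rescue ECMO is already identified through the crossover classification. The team should confirm that ECMO start and stop times are captured in both arms, because the schema in section 6.2 lists the ECMO intervention only for the experimental arm. The remaining drawback is that the exposed group is small and not randomised, which the label makes plain.

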10.3 Evaluation of Efficacy

The efficacy of VV-ECMO will be evaluated by means of assessing delivered tidal volumes in both groups and magnitude of physiological response (reduced driving pressure ΔP) to CO₂ removal by VV-ECMO.

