8.1.2 Maintenance and Weaning of Ultra-Protective Ventilation

Deep sedation, paralysis, and these low-intensity mechanical ventilation settings will be maintained for at least 48 hours after ECMO initiation. The clinical team will make adjustments to the VV-ECMO settings to maintain the same PaCO₂, pH and PaO₂ and SpO₂ targets as above. These adjustments to VV-ECMO sweep gas or blood flow will be dictated by ABG results drawn as clinically indicated.

On study day 3, patients will then enter the maintenance and weaning phase – neuromuscular blockade will be discontinued, and lighter sedation levels (SAS 2-3) will be targeted unless otherwise decided by the attending physician.

During the first 7 days after randomization and once neuromuscular blockade is stopped and patients are making spontaneous breathing efforts, we will use sweep gas flow (primary) and sedation (secondary) to modulate spontaneous efforts to maintain low intensity ventilation, targeting the estimated dynamic trans-pulmonary driving pressure (ΔP_{L-dyn}) and tidal volume.

Clinicians will measure patient respiratory effort by calculating ΔP_{occ} (which is always zero or negative):[26]

- Perform expiratory hold and record trough pressure with next effort (record as = PEEP if no efforts made)
- Calculate $\Delta P_{occ} = \text{trough pressure} - \text{PEEP}$
- Calculate $\Delta P_{L-dyn} = (\text{Peak airway pressure} - \text{PEEP}) - 0.67 \times \Delta P_{occ}$

To maintain $\Delta P_{L-dyn} \leq 23$ cm H₂O while maintaining a V_T of 8 ml/kg PBW or lower, the treating team will adjust in the following order: a) the mechanical ventilator, b) the sweep gas flow, and c) sedation levels. After day 7 driving pressure and V_T targets, as well as sweep gas settings will be determined by the attending physician.

We will wean ECMO prior to liberating from mechanical ventilation and provide explicit protocols for weaning ECMO (See Manual of Procedures). Briefly, patients will be assessed daily for ability to discontinue ECMO – all patients who are not paralyzed and are breathing spontaneously on sweep gas flow of 4 L/min or less, and who are receiving an FiO₂ of ≤ 0.6 on the mechanical ventilator with a PaO₂/FiO₂ > 150 will undergo a trial of sweep gas off on ECMO. ECMO will be discontinued if patients tolerate sweep gas off for at least 12 hours (i.e., no significant hypoxemia, respiratory acidosis, or work of breathing).

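### For at least the first 48 hours of ECMO, the driving-pressure fall that 10.2 and 10.3 treat as a response to CO₂ removal is a ventilator setting, and it is tied to the ECMO group alone

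*Protocol*

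**What the plan says.** Section 10.3 names two efficacy measures. The first is "assessing delivered tidal volumes in both groups". The second is the "magnitude of physiological response (reduced driving pressure" ΔP) to CO₂ removal, with no comparator or time point. Section 10.2 evaluates safety and tolerability by recording SAEs and by "monitoring the predicted physiological response (reduced driving pressure ΔP) to CO₂ removal by VV-ECMO", and then lists complication categories, death and clinical endpoints. Objective 2 in section 4.2 likewise looks at tidal volume in both groups but at driving pressure in the ECMO group.

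The intervention sections say how that driving pressure arises. Under 8.1.1, if "static ΔP is 16 cmH₂O or higher, then proceed with cannulation and connection to the VV-ECMO circuit". Once ECMO is running, the ventilator goes to pressure control with the instruction "Set Driving Pressure to 10". Under 8.1.2, with deep sedation and paralysis, "these low-intensity mechanical ventilation settings will be maintained for at least 48 hours after ECMO initiation", and the team corrects PaCO₂, pH and oxygenation through the ECMO settings.

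The schema in 6.2 records plateau and driving pressure, tidal volume, rate and blood gases (including PaCO₂ and pH) at baseline and daily, in both groups.

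**The concern.** A physiological response is something the patient shows when the intervention works and fails to show when it does not. Here the quantity is set by the clinical team, so during the paralysed phase it cannot separate effective from ineffective CO₂ removal as long as the setting is followed. Inadequate removal would show in PaCO₂ and pH, which are recorded but named in neither 10.2 nor 10.3.

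The background (3.2) gives as the likely reason for the neutral result of an earlier low-flow ECCO₂R trial that ventilation intensity fell only modestly, with driving pressure lower by only 3 cmH₂O. It also argues that driving-pressure reduction is what carries the benefit of smaller tidal volumes. The pilot therefore needs to describe how far driving pressure differs between the randomised groups, and whether CO₂ removal sustained that difference. A fall from baseline in ECMO patients answers neither question. As worded, it also has no natural place for experimental patients who never start ECMO, for example those who stay at 15 cmH₂O or lower on re-assessment.

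**Working it through.** **Inputs from the protocol.** Cannulation threshold: static driving pressure 16 cmH₂O or more (8.1.1). Set value after ECMO start: 10 (8.1.1). Duration: at least 48 hours (8.1.2). Elastance = driving pressure / (tidal volume per kg PBW) (8.1.1). Control limits: plateau pressure 30 cmH₂O or less, tidal volume 6 ml/kg reducible to 4 (8.2).

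**Reproducing the plan's own figure.** Driving pressure 15 at 6 ml/kg gives 15 / 6 = 2.5 cmH₂O/(ml/kg), the elastance limit in 5.3.2. The equation and the eligibility limit agree.

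**Built-in fall.** Fall = baseline − 10, taking the delivered value as the set value in a paralysed patient. Baselines above 16 are assumed for illustration.

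| Baseline driving pressure | Fall | As % of baseline |
|---|---|---|
| 16 (minimum) | 16 − 10 = 6 | 38% |
| 18 | 8 | 44% |
| 20 | 10 | 50% |
| 25 | 15 | 60% |

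The amount of CO₂ removed appears nowhere in this calculation. Differences between patients in the size of the fall are differences in baseline.

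**Where failed CO₂ removal would show.** At baseline 16 and 6 ml/kg, elastance is 16 / 6 = 2.67, so a set pressure of 10 delivers 10 / 2.67 = 3.75 ml/kg. The rate is set to 10. If the previous rate was 25 to 35 (an assumption; 35 is the maximum in 8.1.1), ventilation by the native lung falls by 1 − (3.75 × 10)/(6 × 25) = 75% to 1 − (3.75 × 10)/(6 × 35) = 82%. If the circuit did not make this up, PaCO₂ and pH would move while driving pressure stayed at 10.

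**Why the one-group fall is not the separation.** Controls can also end below their starting value, because 8.2 reduces tidal volume when plateau pressure exceeds 30. Assume PEEP 15, constant elastance and adjustment through tidal volume only; the control driving pressure at plateau 30 is then 30 − 15 = 15.

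- Baseline 16: plateau 16 + 15 = 31. Control tidal volume is 15 / 2.67 = 5.6 ml/kg. The ECMO-group fall is 6; the separation is 15 − 10 = 5.
- Baseline 22: plateau 22 + 15 = 37. Control tidal volume is 15 / (22 / 6) = 4.1 ml/kg. The ECMO-group fall is 12; the separation is 5.

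The gap between the two measures is thus 1 cmH₂O in the first case and 7 in the second. If plateau pressure is not exceeded and controls stay at baseline, the two agree.

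**The case against.** The strongest reply is that this is loose wording around a descriptive measure. Much of that stands.

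- A reader might infer that the measure declares success even if CO₂ removal fails. The protocol does not support this. No threshold is attached to the fall, it is not among the endpoints in 10.5, 10.7 or 10.9, and the criteria in 10.13 are adherence, crossover and accrual. Clinicians departing from the setting could also reveal failure indirectly.
- A reader might infer that the pilot cannot show separation or detect device failure. That also goes too far. Tidal volume is assessed in both groups, driving pressure is recorded daily in both, and 10.2 covers SAEs and mechanical, pulmonary and metabolic complications. Section 9.1 names death or cardiac arrest from device failure among the SAEs of particular interest.
- The construction covers only patients treated per protocol in the early phase. From study day 3 the targets are dynamic trans-pulmonary driving pressure and tidal volume, and after day 7 the attending physician decides.
- It is tempting to say that control care could shrink separation to about 0.7 cmH₂O (2.67 × 4 = 10.7, less 10). That needs plateau pressure to exceed 30 until tidal volume reaches 4 ml/kg, hence PEEP of about 30 − 10.7 = 19.3, and 8.2 also allows lowering PEEP instead. It is not a realistic bound.
- Regression to the mean adds little when the later value is fixed at 10.
- The exclusion of experimental patients who never start ECMO follows from the wording of 10.3 but is not stated, and 10.12 applies intention to treat to its own analyses.
- A between-group difference also largely reflects assigned settings. That is true, but it describes delivered separation correctly and does not attribute it to CO₂ removal.

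A later analysis plan could supply a comparator and time points. It would still inherit a measure that the protocol itself describes as a response to CO₂ removal and ties to the ECMO group.

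**Conclusion.** The point holds in limited form and should be corrected. For at least 48 hours after ECMO start, a patient treated per protocol shows a fall of baseline minus 10, at least 6 cmH₂O, regardless of CO₂ removed. In that phase the fall measures baseline severity and adherence to the setting. As worded it does not describe separation in driving pressure between randomised groups, and it carries little information on tolerability.

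The minimum of 6 rests on the protocol's figures and on the set value being delivered. The 5 cmH₂O separations are illustrations at an assumed PEEP of 15, not forecasts. The importance is moderate: no feasibility decision depends on the fall, but it affects what the pilot can conclude about delivered separation and about CO₂ removal.

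**What to change.** **In 10.3**, replace the fall in driving pressure with a descriptive summary by randomised group, including experimental patients who never start ECMO: the between-group difference in daily driving pressure on days 1-3, next to tidal volume and respiratory rate. Label it delivered separation, not response to CO₂ removal. Beside it, report the recorded PaCO₂ and pH by group. In the experimental group only, add the share of values within that group's stated PaCO₂ target of 40-60 mmHg (8.1.1), since the protocol gives controls no such target. Show patients with baseline PaCO₂ above 60 separately, because 8.1.1 has it lowered slowly and their early values may be out of range while following the protocol.

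**In 10.2**, remove the driving-pressure fall as a safety and tolerability measure and report PaCO₂ and pH by group in its place. The SAEs, complication categories and clinical endpoints stay as they are.

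**Cost.** Rewording of two sections and a few more descriptive tables from data already collected daily in both groups. No treatment rule changes. The downside is that the reported effect may be smaller than the built-in fall.
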